12.5.2.2 Sensitivity Analysis #2 - Robust regression for Sensitivity Analysis of Primary Endpoint

If examination of residual plots indicates clear non-normality, then ALP data at Week 24 will additionally be analyzed using a Robust Regression approach after first multiply imputing any missing data in the same manner as described in 12.5.2.2.1 Step 1. ALP values will be log-transformed prior to analysis. Results will be presented in terms of the ratio of geometric least squares mean values and their associated 95% CI.

Version Date: 27-June-2024 Sponsor: Calliditas Therapeutics Suisse SA

Protocol No: GSN000350

This will be achieved by exponentiating the treatment effect and 95% CI for the mean difference in log-transformed values obtained from the robust regression model for the corresponding timepoint.

Step 1: create data with a monotone data structure having imputed 20 datasets separately within each treatment arm. The number of burn-in iterations will be set to 200, and observations will be sampled every 200 iterations within the same chain for each imputed dataset. An autocorrelation plot will be produced to confirm that NITER is long enough to ensure imputations are independent and a trace plot also produced to confirm there are no systematic trends.

```
proc mi data=data nimpute=20 seed=2019301 out=mono;
var BASE VAL1-VAL6;
mcmc chain=single nbiter=200 niter=200 impute=monotone;
by TRT;
run;
```

Step 2: data will be multiply imputed using a regression method sequentially imputing data across successive visits separately by treatment arm from each dataset imputed in the first step. This analysis assumes data are missing at random conditional on previous ALP recordings, which is the same assumption used in a MMRM model and therefore would be expected to give equivalent results (O'Kelly & Ratitch).

```
proc mi data=mono nimpute=1 SEED=2019301 OUT=imputed; class TRT; var BASE VAL1-VAL5; monotone regression; by TRT _imputation_; run;
```

log-transformed data will be analyzed using Robust Regression with independent variables of treatment and log transformed baseline ALP. M-estimation will be used with Huber weights and a cut-off value of 2 with the median method used to estimate the scale parameter. This approach means that standardized residuals with an absolute value of ≤ 2 , corresponding to the central 95% of the data if normally distributed, have equal weight and outlying data are weighted according to a pre-specified function, Wc (x), which gives lower weights to the most outlying data where Wc (x) = min {1, c / |x| } where x is the standardized residual, corresponding to least square standardized residuals in the first iteration. Given that dependent variables are categorical and inclusion criteria for the only continuous covariate, log-transformed baseline ALP, prevents this variable from having outlying values, M-estimation will be appropriate.

In the pooling phase, estimated treatment effects and associated standard errors from each imputation will be combined using Rubin's rules to provide an overall treatment effect, associated 95% CI, and 1-sided p-value.

```
proc mianalyze data=est1;
modeleffects estimate;
stderr stderr;
ods output ParameterEstimates=est2;
run;
```

Version Date: 27-June-2024 Sponsor: Calliditas Therapeutics Suisse SA

Protocol No: GSN000350

12.5.2.3 Supplementary Analyses

If there are important protocol deviations that impact efficacy, the primary analysis (see Section 12.5.2.1) will be repeated using the PPS. Subjects with important protocol deviations could falsely draw the estimated treatment difference closer. Exclusion of these subjects in this sensitivity analysis will help assess the magnitude, if any, of this effect.

12.5.2.4 Summary of Analyses for the Primary Endpoint

The overview of analyses for the primary endpoint are summarized in the Table below.

Table 7: Summary of Analyses for the Primary Endpoint

Analysis	Popula tion	Method	
Summary of reductions in ALP from baseline at each scheduled time point up to Week 24	FAS	 Cumulative counts for the number of subjects with specific percentage reductions (≥15%, ≥30%, ≥40%, ≥50%, and ≥70%) from baseline Bar chart visualization at each time point by treatment 	
Summary of ALP at each scheduled time point up to Week 24	FAS	Summary Statistics (including geometric mean, geometric standard deviation, median, minimum, and maximum, and geometric mean ratio of ALP to baseline)	
	FAS	 Individual line plots of ALP versus time for each subject by treatment Line plot for geometric mean ALP vs time by treatment Line plot for geometric mean ratio ALP (in % reduction) vs time by treatment 	
Primary Analysis - % change in ALP for each setanaxib dose versus placebo, derived from geometric least squares mean ratios estimated	FAS/PP S	Mixed Model Repeated Measures (MMRM)	
		Forest plot of geometric mean to compare FAS, PPS, Sensitivity Analyses #1 and #2	
Sensitivity Analysis #1 – Deal with missing data	FAS	Multiple Imputation (MAR) + Mixed Model Repeated Measures (MMRM) to provide an overall treatment effect, associated 95% confidence interval (CI), and 1-sided p-value	
Sensitivity Analysis #2 – Assess impact of outliers	FAS	Multiple Imputation (MAR) + Robust Regression	

12.5.3 Secondary Estimands

12.5.3.1 Secondary Analyses

The secondary estimands are:

- To assess the change in fatigue (as assessed by the **PROMIS-short form-Fatigue 7b Daily** and by the **PBC40 fatigue domai**n) over 24 weeks in subjects with PBC, elevated liver stiffness, and intolerance or inadequate response to UDCA. The intercurrent events are as defined for the primary estimand (see Table 5).
- To assess the change in liver stiffness over 24 weeks in subjects with PBC, elevated liver stiffness, and intolerance or inadequate response to UDCA. The intercurrent events are as defined for the primary estimand (see Table 5).
- To assess the change in ALP, fatigue and liver stiffness in subjects with PBC, elevated liver stiffness, and intolerance or inadequate response to UDCA, where both setanaxib doses are

Version Date: 27-June-2024

Sponsor: Calliditas Therapeutics Suisse SA

Protocol No: GSN000350

combined into one setanaxib treatment group. The intercurrent events are as defined for the primary estimand (see Table 5).

The primary analysis methodology described in Section 12.5.2.1 will be repeated for the secondary estimands, with the exception that the outcome variable for analyses of fatigue will be absolute change from baseline (*calculated as postbaseline minus baseline values*) with no log transformation and the baseline covariate in the model will not be log transformed. As described below, Y_{ij} is the observed response (absolute change in fatigue at visit i (up to Week 24) to baseline).

$$Y_{ij} = \beta_0 + \beta_1$$
 · Treatment $_i + \beta_2$ · Visit $_j + \beta_3$ · (Baseline fatigue $_{ij}$) + β_4 · (Baseline fatigue $_{ij}$ × Visit $_j$) + β_5 (Treatment $_i$ × Visit $_j$) + b_i + ϵ_{ij}

For the analysis of fatigue, fatigue data captured at Baseline, Weeks 4, 12, and 24 will be included in the model. Subjects enrolled under protocol version 1.0 and reconsented to version 2.0 will have no baseline value for the PROMIS-short form-Fatigue 7b as this questionnaire was introduced in version 2.0 at the request of the FDA. A sensitivity analysis will be performed with imputation of missing data.

12.5.3.2 Sensitivity Analysis

The sensitivity analysis with multiple imputation defined in 12.5.2.2.1 will be performed for the secondary estimands.

12.5.3.3 Supplementary Analyses

For the combined setanaxib treatment group versus placebo, where there is sufficient data (at least 10 patients at each level of the subgroup within each treatment group), additional *exploratory* analyses examining the consistency of the treatment difference among subgroups using the FAS will be performed. The primary analysis will be repeated at each level of the subgroup. A tabulation at Week 24 will be presented for each of the following subgroups:

- Age group: ≥18 and <65 years, ≥ 65 years
- Sex: Female vs Male
- Actual Randomization Strata: Screening serum ALP < or ≥3.0×ULN
- UDCA use ongoing at Randomization: Yes vs No
- UDCA use prior to or at Randomization: Yes vs No
- OCA use ongoing at Randomization: Yes vs No
- OCA use prior to or at Randomization: Yes vs No
- Fibrate use (bezafibrate or fenofibrate) ongoing at Randomization: Yes vs No

12.5.3.4 Summary of Secondary Analyses

The overview of primary analyses are summarized in Table below.

Table 8: Summary of Secondary Analyses

Version Date: 27-June-2024

Sponsor: Calliditas Therapeutics Suisse SA

Endpoints	Populatio	Analysis	
	n		
Change in fatigue assessed by the PROMIS-short form-Fatigue 7b Daily (3 treatment groups)	FAS	 Summary Statistics of change (and % change) in the PROMIS short form fatigue 7b compared to baseline by time points Line plot for mean of PROMIS short form fatigue 7b vs time point for by treatment 	
	FAS	MMRM Model of absolute change in the PROMIS short form fatigue 7b compared to baseline	
	FAS	Sensitivity Analysis using MCMC monotone imputation	
Change in fatigue assessed by the PBC40 fatigue domain (3 treatment groups)	FAS	Summary Statistics of change (and % change) in the PBC40 fatigue domain compared to baseline Line plot for mean of PBC40 fatigue domain vs time point by treatment	
	FAS	MMRM Model of absolute change in the PBC40 fatigue domain compared to baseline	
	FAS	Sensitivity Analysis using MCMC monotone imputation	
Change in liver stiffness over 24 weeks (3 treatment groups)	FAS	 Summary Statistics of change (geometric ratio) in the liver stiffness compared to baseline Line plot for geometric mean vs time point by treatment 	
	FAS	MMRM Model of change in the liver stiffness compared to baseline	
	FAS	Sensitivity Analysis using MCMC monotone imputation	
Change in fatigue assessed by the PROMIS-short form-Fatigue 7b Daily (combined setanaxib group)	FAS	Summary Statistics of change (and % change) in the PROMIS short form fatigue 7b compared to baseline	
	FAS	MMRM Model of absolute change in the PROMIS short form fatigue 7b compared to baseline	
	FAS	Sensitivity Analysis using MCMC monotone imputation	
Change in fatigue assessed by the PBC40 fatigue domain (combined setanaxib group)	FAS	Summary Statistics of change (and % change) in the PBC40 fatigue domain compared to baseline	
	FAS	MMRM Model of absolute change in the PBC40 fatigue domain compared to baseline	
	FAS	Sensitivity Analysis using MCMC monotone imputation	
Change in liver stiffness over 24 weeks (combined setanaxib group)	FAS	Summary statistics for liver stiffness at each visit (including geometric mean, geometric standard deviation, median, minimum, and maximum) Summary of geometric ratio of liver stiffness compared to baseline by time point	
	FAS	MMRM Model of change in the liver stiffness compared to baseline	
	FAS	Sensitivity Analysis using MCMC monotone imputation	
Change in ALP up to Week 24 (combined setanaxib group)	FAS	Summary Statistics (including geometric mean, geometric standard deviation, median, minimum, and maximum) Summary of geometric ratio of ALP compared to baseline by time point	
	FAS	MMRM Model of change in the ALP compared to baseline	

Sponsor: Calliditas Therapeutics Suisse SA

Protocol No: GSN000350

	FAS	Sensitivity Analysis using MCMC monotone imputation
Change in ALP up to Week 24 (combined setanaxib group) by Subgroup	FAS	MMRM Model of change in the ALP compared to baseline (performed at least 10 patients at each level of the subgroup within each treatment group)
 Age Sex Actual Randomization Strata UDCA use ongoing at Randomization UDCA use prior to or at Randomization OCA use ongoing at Randomization 		
 OCA use prior to or at Randomization Fibrate use (bezafibrate or fenofibrate) ongoing at Randomization 		

12.5.4 Other Secondary Endpoints Analyses

For the secondary endpoints listed below, summary statistics for each scheduled timepoint will be presented. These will include the arithmetic mean, standard deviation, geometric mean, geometric mean, +/- geometric standard deviation, median, minimum, maximum. For the % change, if the data are lognormally distributed, the ratio of post-baseline result to baseline will be calculate for each scheduled timepoint and a logarithmic transformation applied.

The mean and mean +/- standard deviation and mean +/- standard error of the log ratios will be calculated. The results will be back-transformed to get the geometric mean ratio (+/- geometric standard deviation and +/- geometric SE for graphical purposes). These results will be converted to the % scale and plotted as a line graph for each treatment group. Values after initiation of PBC-related medication will be treated as missing values at the analysis visit following initiation of the medication. Summary tables will include scheduled visit out to Week 52 + EoT (noting that the number of subjects will be small beyond week 24), but graphs will display data for the 24-week treatment period only.

- Change in PGIS fatigue at Week 24 compared to baseline
- PGIC fatigue by time point
- Change in WI-NRS compared to baseline
- Change in PBC-40 itch compared to baseline
- Change in PGIS pruritus compared to baseline
- PGIC pruritus by time point

12.5.4.1 Markers of Cholestasis at Week 24

To summarize the changes in markers of cholestasis, the number and percentage of subjects at each scheduled timepoint meeting the following criteria for FAS will be presented:

- ALP reduction to <1.67×ULN and total bilirubin ≤1xULN and a ≥15% or ≥30% or ≥40% or ≥70% ALP reduction from Baseline, respectively
- ALP reduction to <1.5×ULN and total bilirubin ≤1xULN and with a ≥40% ALP reduction from Baseline
- ALP reduction to <1xULN and total bilirubin reduction to ≤1xULN
- Total bilirubin reduction to <0.6×ULN

Version Date: 27-June-2024

Sponsor: Calliditas Therapeutics Suisse SA

Protocol No: GSN000350

Descriptive proportions will be presented for all scheduled time points up to Week 24. Subjects who start a PBC-related medication will be considered a non-responder at the time point after initiation of the PBC medication. Subjects who experience and adverse clinical outcome prior to Week 24 will also be considered non-responders.

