#### 8.4.1.5 Secondary Endpoints

The secondary efficacy endpoints, as appropriate, will be analyzed using the same approach as the primary analysis.

As additional secondary endpoints, the 2 setanaxib dose arms will be combined for the analysis of change in ALP (%), change in fatigue, and change in liver stiffness and will be analyzed per the primary endpoint.

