Q1	Never=5; Rarely=4; Sometimes=3; Most of the time=2; Always=1
Q2, Q4-Q7	Never=1; Rarely=2; Sometimes=3; Most of the time=4; Always=5
Q3	Never=1; Rarely=2; Sometimes=3; Most of the time=4; Always=5; Did not apply/never drink alcohol=0
Itch (3)	Range: 0 to 15

Sponsor: Calliditas Therapeutics Suisse SA

Protocol No: GSN000350

Domain (No of questions)	Response Score
Q8-Q10	Never=1; Rarely=2; Sometimes=3; Most of the time=4; Always=5; Did not apply/no itch=0
Fatigue (11)	Range: 11 to 55
Q11-Q21	Never=1; Rarely=2; Sometimes=3; Most of the time=4; Always=5
Cognitive Function (6)	Range: 6 to 30
Q22-Q27	Never=1; Rarely=2; Sometimes=3; Most of the time=4; Always=5
Social Function (10)	Range: 8 to 50
Q29, Q31	Not at all=1; A little=2; Somewhat=3; Quite a bit=4; Very Much=5; Does not apply=0
Q32	Not at all=1; A little=2; Somewhat=3; Quite a bit=4; Very Much=5;
Q34-Q39	Strongly agree=5; Agree=4; Neither agree not disagree=3; Disagree=2; Strongly disagree=1
Q40	Strongly agree=1; Agree=2; Neither agree not disagree=3; Disagree=4; Strongly disagree=5
Emotional Function (6)	Range: 3 to 15
Q28, Q30, Q33	Not at all=1; A little=2; Somewhat=3; Quite a bit=4; Very Much=5

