10.14 Worst Itch Numerical Rating Scale

The WI-NRS is a daily patient-reported measure of itch intensity using an 11-point scale (where 0=no itch and 10=worst itching imaginable). The WI-NRS will be completed and collected via daily diary over 7 days prior to the visits.

The WI-NRS score for baseline and post-baseline visits will be calculated by averaging the daily WI-NRS scores before the visit date (inclusive). The calculation of this average value will proceed only if 4 or more daily scores are available; otherwise, the final score will be treated as missing for the corresponding visit. The baseline WI-NRS score will be defined as the mean of the daily WI-NRS scores over the last 7 days prior to first treatment administration. For post-baseline assessments only, if data over 8 days is collected, all 8 days will be included in the calculation of the average value.

Version Date: 27-June-2024

Sponsor: Calliditas Therapeutics Suisse SA

Protocol No: GSN000350

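### SAP 12.5.4 applies geometric statistics to two itch scales that include a true zero, with no zero rule, and the SAP gives pruritus, a secondary objective, no between-arm estimate

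*SAP*

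**What the plan says.** **Summary statistics.** SAP 12.5.4 covers six patient-reported endpoints: WI-NRS, PBC-40 itch, and PGIS and PGIC for both fatigue and pruritus. The itch diary appears as "Change in WI-NRS compared to baseline". One list of statistics serves all six and carries no condition: "These will include the arithmetic mean, standard deviation, geometric mean, geometric mean, +/- geometric standard deviation, median, minimum, maximum".

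**Percent change.** The section continues: "For the % change, if the data are lognormally distributed, the ratio of post-baseline result to baseline will be calculate for each scheduled timepoint". The log ratios are then averaged and back-transformed, and "These results will be converted to the % scale and plotted as a line graph for each treatment group". It does not say how lognormality will be judged or what replaces the ratio if it fails.

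**The itch scales.** SAP 10.14 describes WI-NRS as measured "using an 11-point scale (where 0=no itch and 10=worst itching imaginable". In SAP 10.12 each of the three PBC-40 itch items has the option "Did not apply/no itch=0", and the domain runs from 0 to 15. The limit-of-quantification rule in SAP 10.17 concerns safety assessments. No section says how a questionnaire score of zero enters a logarithm.

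**Pruritus as an objective.** Its effect at Week 24 is a secondary objective (Protocol 2.2, SAP 7.2). Protocol 8.4.1.5 states: "The secondary efficacy endpoints, as appropriate, will be analyzed using the same approach as the primary analysis". Protocol 8.4.1.2 and SAP 12.5.1 both say that nominal p-values will be presented for secondary endpoints. Yet SAP 12.0 confines formal testing to ALP, fatigue and liver stiffness, the summary table in SAP 12.5.3.4 has no pruritus row, and SAP 12.5.4 contains no model. SAP 6.1 lists two changes from the protocol, and this is not one of them.

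**Fatigue, for comparison.** In SAP 12.5.3.1, "the outcome variable for analyses of fatigue will be absolute change from baseline", without log transformation.

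**The concern.** The statistics in SAP 12.5.4 suit a strictly positive laboratory value such as ALP. On the two itch scales the best possible result is 0, where the logarithm does not exist. A programmer who follows the text must choose between a missing value, a geometric mean of 0, dropping the patient, or an unplanned offset, and these give very different numbers. If zeros are dropped, the set of patients behind the column also changes from visit to visit, and changes most in the arm where itch resolves most often.

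Zero baselines raise the same problem, because a baseline of 0 has no ratio and no percent change. No entry criterion in Protocol 4.1 or 4.2 requires itch, and Protocol 1.1.1 notes that up to 60% of patients are asymptomatic at diagnosis. Zero baselines are therefore plausible.

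The second issue is what the trial can say about pruritus. Protocol 1.1.1.1 notes that an approved PBC drug worsens it, and the sponsor's earlier PBC study compared itch with placebo (Protocol 1.1.4). Under this SAP, pruritus gets by-arm description only, whereas the PROMIS-29 fatigue domain, an exploratory endpoint, gets an MMRM (SAP 12.5.5.2).

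**Working it through.** The plan gives no power or sample-size figure for itch to reproduce. The one stated figure that can be checked is the PBC-40 itch range.

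**1. Can the scores be zero?**
- PBC-40 itch: 3 items × 0 = 0 and 3 × 5 = 15, which matches the stated range. Answering never to all three gives 3 × 1 = 3, so a domain score of 0 needs the does-not-apply/no-itch option on every item.
- WI-NRS: the visit score averages at least 4 daily scores (SAP 10.14). It is 0 only if every available day is 0.
- PGIS runs 1 to 5 and PGIC 1 to 7 (SAP 10.15). Neither has a zero.

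Zero is reachable on both itch scales, though not by an occasional itch-free day.

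**2. The unconditional geometric mean.** GM = exp(mean of ln x). Assumed data, since the documents give no itch distribution: 16 patients (the evaluable number per arm in SAP 8.1), all with baseline 5. At Week 24, k are at 0 and the rest at 4.

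| k at 0 | Arithmetic mean | Mean change | GM, zeros kept | GM, zeros dropped (n used) |
|---|---|---|---|---|
| 0 | 4.0 | −1.0 | 4.0 | 4.0 (16) |
| 1 | 3.75 | −1.25 | 0 | 4.0 (15) |
| 4 | 3.0 | −2.0 | 0 | 4.0 (12) |
| 8 | 2.0 | −3.0 | 0 | 4.0 (8) |

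Mean change = [k × (−5) + (16 − k) × (−1)] / 16. For k = 4 this is (−20 − 12)/16 = −2.0. The geometric column either collapses at the first zero or does not respond to resolution at all.

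**3. The conditional ratio.** GMR = exp(mean of ln(post/baseline)). With zeros dropped, GMR = 4/5 = 0.80, or −20%, for every k in the table. With zeros kept it is −100% from k = 1. An offset does not settle it. For k = 4:
- adding 1: exp{[12 ln(5/6) + 4 ln(1/6)]/16} = 0.557, or −44%
- adding 0.1: exp{[12 ln(4.1/5.1) + 4 ln(0.1/5.1)]/16} = 0.318, or −68%

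Data containing zeros are not lognormal, so a strict reading of the SAP condition would not take this branch. The gap is that no criterion is given and no alternative is named.

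**4. Would a between-arm estimate be usable?** Half-width of the 95% CI = t(0.975, 30 df) × SD × √(2/16). The documents give no SD for WI-NRS change. For an assumed SD of 1.5 to 3.0 points the half-width is about 1.1 to 2.2 points, which is estimable but imprecise. Both itch scales are collected at Baseline and Weeks 4, 12 and 24 (Protocol Table 1), the visits used in the fatigue model.

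**The case against.** The strongest reply is that little depends on the geometric columns. The same list contains the arithmetic mean, SD, median, minimum and maximum, SAP 12.0 adds n and quartiles by default, and SAP 10.1.5 defines change as post-baseline minus baseline. A patient who reaches 0 stays in all of these. That stands. A reader might infer that patients whose itch resolves are lost from the pruritus results generally, and the documents do not support that.

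Nor do they support reading the −20% or −100% above as what the percent graph will show, because the graph is conditional on lognormality. The frequency of zeros is not documented, and the zero problem does not reach PGIS or PGIC.

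The untransformed fatigue analysis might look like evidence that the SAP's authors had already recognised the problem. It is not. PBC-40 fatigue runs 11 to 55 and the PROMIS T-scores 31.0 to 81.4, neither scale has a zero, and the SAP gives no reason for the choice.

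On the missing estimate, the defence is that SAP 12.0 makes a stated choice of scope, that Protocol 8.4.1.5 is qualified and leaves room for description, and that an unadjusted difference with an interval can be computed from the reported n, mean and SD. All three are fair. It would therefore be too strong to say that the SAP breaches the protocol or that the trial cannot produce an itch difference. What remains is that both documents say nominal p-values will be presented for secondary endpoints, pruritus gets none, and SAP 6.1 does not record the narrowing.

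**Conclusion.** The point holds in two limited parts.

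First, the geometric mean and geometric SD are planned unconditionally for WI-NRS and PBC-40 itch, both of which include a true 0, with no zero rule. Those columns will be undefined, zero or computed on a changing subset wherever a 0 occurs. The log-ratio summary and percent graph add a condition with no criterion and no fallback. The damage is confined to the geometric columns and possibly the graph. No primary result, formal test or arithmetic summary is affected. The size shown (geometric mean fixed at 4.0 while the arithmetic mean halves from 4.0 to 2.0) rests on invented data and illustrates the mechanism; it does not forecast the result.

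Second, pruritus is a secondary objective for which the SAP specifies no between-arm difference, interval or p-value. This is an unrecorded narrowing rather than a clear contradiction of the protocol. The plan should be changed because the remedy is cheap and would let the trial answer its own question on itch.

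**What to change.** In SAP 12.5.4, for WI-NRS and PBC-40 itch:

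1. Delete the geometric mean, geometric SD and log-ratio/percent graph. Summarise and plot arithmetic absolute change from baseline, keeping the median.
2. Fit the absolute-change MMRM of SAP 12.5.3.1 (Weeks 4, 12 and 24) to each scale. Report the difference versus placebo for each dose, with 95% CI and nominal p-value.
3. If the sponsor prefers to keep pruritus descriptive, record that in SAP 6.1 as a change from the protocol and still make the first edit.

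Category displays for PGIS and PGIC are an optional presentation choice.

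**Cost.** SAP text and reuse of the fatigue program, with no new data. It adds two more endpoints with nominal, unadjusted and imprecise estimates. Subjects enrolled under protocol version 1.0 have no WI-NRS baseline (SAP 10.1.2). SAP 10.11 puts that group at about 15 for the PROMIS fatigue form introduced at the same time. SAP 10.1.2 mentions imputing these baselines, but the imputation table in SAP 10.18 has no WI-NRS row, so as things stand they would drop out of the WI-NRS model and widen its intervals. They stay in the PBC-40 itch model, because SAP 10.1.2 accepts their PBC-40 baseline.
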